1.4 Clinical Experience

As of 20th April 2021, a total of 169 patients with relapsed/refractory hematological malignancies (viz. CLL, PTCL, CTCL and iNHL) have been exposed to tenalisib in either single agent or combination studies; 35 patients in RP6530-1301 study, 58 patients in RP6530-1401 study, 2 patients in RP6530+Pembrolizumab-1701 study, and 33 patients RP6530+Romidepsin-1805 study, 20 patients in RP6530-1802 study, 21 patients in RP6530-1901 study. A total of 16 patients have been rolled over to compassionate study (RP6530-1803); 4 from RP6530-1401 study, 5 from RP6530+Romidepsin-1805 study and 7 from RP6530-1901 study. In addition, 18 healthy volunteers were exposed to tenalisib in food effect study (RP6530-1501).

• Safety:

169 patients have received tenalisib at doses ranging from 25-1200 mg BID. Tenalisib is generally well tolerated in patients with hematological malignancies (at doses ranging from 25 mg BID to 1200 mg BID) and aggressive lymphomas such as TCL (at doses ranging from 200 mg BID to 800 mg BID). The most frequently reported related AEs (all grades) that occurred in more than 10% of patients included alanine aminotransferase (ALT) increased, aspartate aminotransferase (AST) increased (15.6% each) and diarrhea (11.9%). The most frequently reported related Grade ≥3 AEs were ALT increased, AST increased (7.4% each) and neutropenia (4.4%). Other Grade ≥3 laboratory abnormalities included gamma-glutamyl transferase (GGT) increased, International normalized ratio (INR)

CONFIDENTIAL Page 19 of 66

increased, hyperglycemia and hypertriglyceridemia reported in one patient each. Hypophosphatemia and thrombocytopenia were reported in two patients.

Pharmacokinetics:

In RP6530-1301 study, pharmacokinetics (PK) was evaluated in patients with hematological malignancies at doses ranging from 25-1200 mg BID and in TCL at doses ranging from 200 to 800 mg BID. Maximum systemic exposures assessed by AUC_{0-t} as determined on Cycle 1 Day 1 (C1D1) were found at these doses. Tenalisib showed rapid absorption (between 0.5 and 2 h), with C_{max} and AUC_{0-t} increasing proportionately with dose on C1D1. There was no significant accumulation between C1D1 and C2D1. Trough concentrations did not show any specific trends from one day to the other even though concentrations increased generally with doses. $T_{1/2}$ were similar for all dose levels.

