Clinically relevant concentrations of IN0385, a major metabolite of tenalisib, were observed in patients treated with tenalisib. Exposures (C_{max}) for IN0385 ranged between 1.2 to 2.2 times of tenalisib (the parent compound). Elimination kinetics of IN0385 were however similar to tenalisib with half-life ranging between 2 - 4.5 hours.

• Efficacy:

In Phase I study (RP6530-1301 study) in hematological malignancies, two patients (6.5 %) showed CR and 4 patients (12.9%) showed PR in 31 efficacy evaluable patients. The ORR was 19.4 % with a DCR of 61.3%. Duration of response was 5.68 (1.5-15.7) months. The time to onset of response was 3.49 months (1.4-11.9 months). PFS was 4.62 months (1.0-17.5 months).

In patients with TCL (RP6530-1401 study), a total of 16 out of 35 evaluable patients responded to tenalisib with ORR of 45.7% and a median DOR being 4.37 months. The best response of CR was noted in a total three (8.6%) patients while PR was noted in 13 (37.1%) patients. The ORR among CTCL and PTCL patients were similar and were 45.0% and 46.7% respectively. The median DOR among PTCL patients was 4.9 months whereas it was 3.83 months in CTCL patients.

In patients with indolent NHL (RP6530-1802 study), 20 patients received tenalisib in Part 1. Only one FL patient showed a PR out of 19 evaluable patients in the study. In patients with CLL (RP6530-1901 study), seven patients showed PR with ORR of 33% in 21 evaluable patients of Part I. Remaining 14 patients showed a stable disease. The median DOR was 5.23 months.

CONFIDENTIAL Page 20 of 66

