6.4 Laboratory Investigations

Laboratory tests for hematology, chemistry and urinalysis are specified in **Table 3**.

Table 3: Laboratory Tests for Hematology, Chemistry and Urinalysis

| Hematology | Chemistry Panel I | Chemistry Panel II | Urinalysis | Other |
|-------------------------------|--------------------------|--------------------|-------------------|-----------------------|
| Hematocrit | Total bilirubin | Total Cholesterol | Blood | Serum β-hCG |
| Hemoglobin | Alkaline phosphatase | Triglyceride (TG) | Glucose | Urine pregnancy test |
| Platelet count | ALT | LDL | Protein | PT and INR |
| WBC (Total and differentials) | AST | HDL | Specific gravity | Serology (Hepatitis |
| | LDH | T3, T4, TSH | Microscopic | B, Hepatitis C, HIV)- |
| Absolute | | | exam ^b | Historical data is |
| neutrophil count | GGT |  | | acceptable. |
| - | Blood glucose | | | |
| | Albumin | | | |
| | Total protein | | | |
| | Urea or BUN ^a | _ | | |
| | Creatinine | | | |
| | Sodium | | | |
| | Potassium | | | |
| | Calcium | | | |
| | Phosphorous | | | |
| | Chloride | | | |

^a Blood Urea Nitrogen is preferred, if not available Urea may be tested.

NOTE: Laboratory results obtained during Screening should be used to determine eligibility criteria. In situations where laboratory results are out of reference range, the

CONFIDENTIAL Page 35 of 66

^b Microscopic exam, if abnormal results are noted

investigator may opt to retest the patient and the subsequent within range screening result may be used to confirm eligibility.

Blood drawn for these tests will be specified in informed consent form (ICF) as per the site ICF requirements. *All safety laboratory investigations will be performed locally at the site*. Screening labs will be done within 7 calendar days prior to the initiation of trial treatment. If these initial examinations are obtained within 72 hours of Cycle 1 Day 1, the labs need not be repeated on C1D1 again.

6.5 12-Lead Electrocardiograms

A single 12-lead electrocardiogram (ECG) will be obtained at designated time points using local ECG machine that automatically calculates the heart rate and measures PR, QRS, QT, and corrected QT (QTc) intervals. ECG will be performed after the patient has at least a 5-minute rest. Additional ECGs will be obtained if clinically indicated.

Table 4 : ECG time points

| Days | Time points | |
|-------------|--------------------------------------|--|
| Screening | Within last 28 days | |

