| C1D1 | Pre-dose | |
| At other | Pre-dose C2D1, C3D1 and at EOT visit | |
| time points | | |

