- 10. The tests must be done ≤ 7 days prior to initiation of treatment. However, if initial examination is obtained within 72 hours of C1D1; this does not have to be repeated. This test will be performed at supplementary visits if clinically indicated.
- 11. Blood will be collected in all patients for serum cytokine/chemokine estimation at screening (baseline) and at C3D1.
- 12. This is required for women of child-bearing potential. A serum pregnancy test will be performed at screening and 72 hours prior to dosing. Urine pregnancy test will be performed at other visits as indicated.
- 13. ECGs will be performed at screening and C1D1 pre-dose to establish baseline cardiac activity. Additional ECGs will be obtained if clinically indicated. All ECGs will be performed on local equipment.
- 14. A tumour biopsy will be performed in 10-12 patients who have consented for the biopsy. The biopsy will be done after eligibility confirmation prior to the first dose on C1D1. A second tumour biopsy sample will be taken at C3D1.
- 15. CT and/ or MRI will be performed at the time of screening within 28 days of screening. Disease will be re-assessed at C3D1 (± 7 days) and approximately 8 weeks thereafter (± 7 days), and/or at the EOT (not required if done within last 28 days) and/or as clinically indicated (if clinical progression is

CONFIDENTIAL Page 39 of 66

- suspected). If a CR or PR is noted, confirmatory scans should be performed at least 4 weeks after the initial response was first documented. Tumour imaging should remain consistent throughout the study and should include those thought by investigator to best capture status of disease. (Baseline scan, if already available as SOC within 28-days of screening is accepted as part of study protocol). Any other sites at which new disease is suspected should also be appropriately imaged.
- 16. Bone scan will be done at the baseline when progression in bone is suspected. Bone scans need to be repeated only when complete response is reported in target disease or when progression in bone is suspected.
- 17. Tenalisib will be dispensed in a HDPE container having 30 tablets of tenalisib.
- 18. Tenalisib will be administered orally twice a day in 28-days of cycle. Tenalisib will be continued in patients experiencing clinical benefit for 24 months unless progression of disease or toxicity is observed warranting discontinuation of therapy.

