6.6.3 Other Observations Related to Safety

Vital Signs

Absolute value of vital signs parameters will include summaries for systolic and diastolic blood pressure, temperature, pulse, respiratory rate and weight.

Vitals will be done prior to the administration of study treatments, at the time points specified in schedule of events.

Electrocardiogram (ECG)

Absolute value of ECG parameters will include summaries for heart rate, PR, QRS, QT, and QTcF intervals.

Physical Examination

The investigator/qualified designee will perform a complete physical exam during the screening period and as defined in Schedule of Events. Physical examination will include systemic examination (General Appearance, HEENT, neck, cardiovascular, lungs, abdomen, lymph nodes, genitourinary (as applicable), extremities, neurological, skin, and musculoskeletal). Physical examination also includes measurement of accessible nodes and the size of the spleen and liver.

- **ECOG Performance Status**
- Medical and Surgical History
- **Prior and Concomitant Medications**

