Visit/	Actual values	Change from baseling	ne Actual values	Change from baseline	Actual values	Change from baseline
Statistics		values		values		values
Baseline						
N	XX		XX		XX	
Mean	x.xxx		X.XXX		X.XXX	
SD	x.xxxx		X.XXXX		X.XXXX	
Median	x.xxx		X.XXX		X.XXX	
Min, Max	X.XX, X.XX		x.xx, x.xx		x.xx, x.xx	
Cycle 1 Day 1						
N	XX	XX	XX	XX	XX	XX
Mean	x.xxx	X.XXX	X.XXX	X.XXX	X.XXX	X.XXX
SD	x.xxxx	X.XXXX	X.XXXX	X.XXXX	X.XXXX	X.XXXX
Median	x.xxx	X.XXX	X.XXX	X.XXX	X.XXX	X.XXX
Min, Max	x.xx, x.xx	X.XX, X.XX	x.xx, x.xx	x.xx, x.xx	x.xx, x.xx	x.xx, x.xx

Continue for all visits and parameters

The baseline measurement is the last pre-treatment measurement taken on or before Cycle 1 Day 1

Only scheduled visits are included in the table.

EOT: End of Treatment; NE: Non-Estimable.

Reference Listing 16.2.x.x

Program: xx.sas Table Generation: ddmmmyyyy hh:mm:ss

Use same format for

Table 14.3.2.2 Descriptive Summary of Biochemistry parameters - Safety Analysis Set

CONFIDENTIAL Page 55 of 106 Document Date: 12MAY2023. ST-AD-032 version 01

Page xx of yy

Table 14.3.3.1 Descriptive Summary of Vital Signs - Safety Analysis Set

Note - Please remove the column for change from baseline.

Add footnote-"Vitals is collected at Pre-dose during treatment visits"

Table 14.3.4.1 Descriptive Summary of ECG - Safety Analysis Set

Document Date: 12MAY2023.

Note - Please remove the column for change from baseline.

Add footnote-"ECG is collected at Pre-dose during treatment visits"

Protocol RP6530-2101 Table 14.3.4.2 Summary of Abnormal ECG results Safety Analysis Set Page xx of yy

		Tenalisib 800 mg BID	Tenalisib 1200 mg BID	Overall
Visit	Criteria	(N=xx)	(N=xx)	(N=xx)
		n (%)	n (%)	n (%)
Baseline	Clinically significant	xx (xx.x)	xx (xx.x)	xx (xx.x)
	Not clinically significant	xx (xx.x)	xx (xx.x)	xx (xx.x)
Cycle 1 Day 15	Clinically significant	xx (xx.x)	xx (xx.x)	xx (xx.x)
	Not clinically significant	xx (xx.x)	xx (xx.x)	xx (xx.x)
Cycle 2 Day 1	Clinically significant	xx (xx.x)	xx (xx.x)	xx (xx.x)
	Not clinically significant	xx (xx.x)	xx (xx.x)	xx (xx.x)
Cycle 2 Day 15	Clinically significant	xx (xx.x)	xx (xx.x)	xx (xx.x)
	Not clinically significant	xx (xx.x)	xx (xx.x)	xx (xx.x)
Cycle 3 Day 1	Clinically significant	xx (xx.x)	xx (xx.x)	xx (xx.x)
	Not clinically significant	xx (xx.x)	xx (xx.x)	xx (xx.x)
Cycle 3 Day 15	Clinically significant	xx (xx.x)	xx (xx.x)	xx (xx.x)
•	Not clinically significant	xx (xx.x)	xx (xx.x)	xx (xx.x)
Continue for all visit	ts			

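### No scheduled ECG falls near tenalisib's 0.5–2 h peak, so a concentration-driven QTcF effect would be largely missed, and the SAP drops change from baseline

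*Protocol*

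**What the plan says.** **Schedule.** Protocol 6.5 and Table 4 set ECGs at screening, C1D1 pre-dose, then "Pre-dose C2D1, C3D1 and at EOT visit". Table 5 marks the same visits, and its footnote 13 gives the purpose of the first two: "ECGs will be performed at screening and C1D1 pre-dose to establish baseline cardiac activity". Each is one tracing on a local machine: "A single 12-lead electrocardiogram (ECG) will be obtained at designated time points". Unscheduled tracings are allowed: "Additional ECGs will be obtained if clinically indicated". Protocol 6.8 puts EOT within 7 days of the last dose or discontinuation. Nothing is scheduled between C3D1 (day 57) and EOT, although treatment may run for 24 months.

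**Pharmacokinetics.** Protocol 1.4 reports "Tenalisib showed rapid absorption (between 0.5 and 2 h", dose-proportional exposure and no significant accumulation. For the major metabolite: "Elimination kinetics of IN0385 were however similar to tenalisib with half-life ranging between 2 - 4.5 hours". Its peak concentration is 1.2 to 2.2 times the parent's, but its time to peak is not given.

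**Analysis.** Protocol 9.4.2 lists ECG among the safety endpoints, summarised by dose cohort without inference. SAP 6.6.3 says: "Absolute value of ECG parameters will include summaries for heart rate, PR, QRS, QT, and QTcF intervals". For Table 14.3.4.1 the programmer is told: "Note - Please remove the column for change from baseline". SAP 8.8.4 adds a by-dose table of abnormal ECGs including baseline, and Listing 16.2.11.1 gives each patient's QTcF by visit. SAP 6.5 marks drug concentrations as not applicable.

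**The concern.** Protocol 1.5.2 says the trial is meant to pick between 800 and 1200 mg BID on efficacy signal and acceptable safety. The protocol treats QTcF as relevant: significant prolongation is an exclusion criterion, and QTcF is a named SAP variable. Yet every on-treatment-visit ECG is taken just before a dose, when a drug with a short half-life is at its lowest, and EOT comes after dosing has stopped. If QTcF follows concentration, the ECG tables could look clean in both arms whatever happens at peak, and a reader might take that as cardiac reassurance.

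The analysis adds a smaller gap. Laboratory values get change from baseline (SAP 6.6.2 and 8.8.3). ECG values do not, although two drug-free tracings per patient are collected for that purpose and no reason is given for the difference.

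**Working it through.** The documents give no ECG sample size, power or precision, so there is no figure of theirs to reproduce. The check asks how much drug is present at each scheduled ECG.

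**Inputs from Protocol 1.4, 3.4.3 and 6.8**
- Time to peak, Tmax: 0.5–2 h (the stated absorption time, read as time to peak; parent only).
- Half-life: 2–4.5 h (stated for the metabolite, with the parent described as similar).
- Dosing: twice daily; the missed-dose rule sets an 8 h minimum between doses.
- EOT: 0–7 days after the last dose.

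**Assumptions.** A nominal 12 h interval, inferred from BID, and first-order decline after the peak.

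**Step 1. Share of peak left before the next dose** = 2^(−(interval − Tmax) / half-life)

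| Interval | Half-life | Tmax 0.5 h | Tmax 2 h |
|---|---|---|---|
| 12 h | 2 h | 2^(−11.5/2) = 1.9% | 2^(−10/2) = 3.1% |
| 12 h | 4.5 h | 2^(−11.5/4.5) = 17.0% | 2^(−10/4.5) = 21.4% |
| 8 h | 2 h | 2^(−7.5/2) = 7.4% | 2^(−6/2) = 12.5% |
| 8 h | 4.5 h | 2^(−7.5/4.5) = 31.5% | 2^(−6/4.5) = 39.7% |

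So about 2–21% of peak remains at a 12 h trough, and about 7–40% at the shortest permitted interval.

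**Step 2. EOT**, with Tmax 2 h. At 24 h: 2^(−22/2) = 0.05% to 2^(−22/4.5) = 3.4%. At 48 h: at most 2^(−46/4.5) = 0.08%. At 7 days: effectively nil. An EOT ECG on the day of the last dose could see more.

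**Step 3. Scheduled ECGs timed to the documented peak window:** none of the five (screening, C1D1, C2D1, C3D1, EOT).

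**Step 4. Illustration.** The documents give neither a QTcF standard deviation nor an effect size. Assume SD 10–20 ms and a 20 ms effect at peak on 1200 mg BID, linear in concentration.
- Effect at a 12 h trough: 20 × 0.019 to 20 × 0.214 = about 0.4–4.3 ms.
- 90% CI half-width for one arm's mean, n = 20: 1.645 × SD / √20 = 3.7 ms (SD 10) to 7.4 ms (SD 20). Over most of the range the trough effect lies inside the noise.
- Difference between doses at peak: 20 − 20 × 800/1200 = 6.7 ms. Power with 20 per arm (two-sided 0.05) is 56%, 29% and 18% for SD 10, 15 and 20.
- Difference between doses at trough: 0.1–1.4 ms, with about 3–7% power, counting rejections in the right direction only.
- Smallest between-dose difference detectable with 80% power: (1.960 + 0.842) × SD × √(2/20) = 8.9 ms (SD 10) to 17.7 ms (SD 20).

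Moving the ECG to the peak recovers the effect within each arm. It does not turn the trial into a reliable QTcF comparison of the two doses.

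**The case against.** **Stronger readings a reader might infer, which the documents do not support**
- *A dose-related QTcF effect cannot be seen at all.* Absolute QTcF and abnormal ECGs are tabulated by dose and visit, including baseline, and clinically indicated ECGs are allowed. An effect persisting to trough could appear.
- *ECGs are always taken with little or no drug on board.* That fits a 2 h half-life. At 4.5 h, 17–21% of peak remains at 12 h, and more at 8 h. Seven days is only the outer limit for EOT.
- *Removing the change column hides the effect.* QTcF is listed per patient from screening on, so change can be derived. This is a reporting gap, whereas a missing near-peak tracing cannot be recovered in analysis.
- *The ECG table is offered as cardiac reassurance.* Neither document says so.

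**Other points against**
- No QT signal is reported. Protocol 1.4 covers 169 patients at up to 1200 mg BID and names no cardiac event. The Investigator's Brochure may hold near-peak ECGs from earlier studies; it is not available here, so this settles nothing either way.
- The 0.5–2 h window is the parent's. The metabolite, with the higher peak concentration, may peak at another time.
- Doses are taken one hour before a meal, so part of the window falls after food. A peak-minus-baseline difference would mix drug, meal and clock time.
- SAP 5.1 says the study was closed early, so retiming may no longer be possible.

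These points limit the reach of the finding and shape the remedy. None of them supplies a scheduled ECG near the peak.

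**Conclusion.** The point holds as a cheap improvement. No scheduled ECG falls near the parent drug's documented peak, so a concentration-driven QTcF effect would be largely missed at either dose. With no concentration data, no exposure–response analysis can make up for it. Separately, the SAP plans no QTcF change-from-baseline summary although the baselines are collected.

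The size rests on three assumptions: the stated absorption time is time to peak, decline is first-order, and the interval is 12 h (2–21% of peak) or at shortest 8 h (7–40%). For the metabolite the share cannot be computed. The millisecond and power figures are illustrations on assumed values.

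**What to change.** 1. **Protocol Table 4 and Table 5 footnote 13.** Take the existing C2D1 and C3D1 ECGs within 0.5–2 h after a morning dose taken in clinic, before the meal where possible, and record dose and ECG times. Keep screening and C1D1 pre-dose as baseline. Confirm that the window also suits IN0385. Align the pre-dose footnotes in SAP Tables 14.3.4.1 and 14.3.4.2 and Listings 16.2.11.1 and 16.2.11.2.
2. **SAP 6.6.3, 8.8.4 and Table 14.3.4.1.** Restore change from baseline for QTcF by dose group.
3. **If ECG collection is already complete,** make change 2 and state in the report that every scheduled on-treatment-visit ECG was pre-dose, so no conclusion about a peak QTcF effect or cardiac safety at peak is drawn for either dose.

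**Cost.** No extra ECG or visit: Table 5 already marks tenalisib administration at C2D1 and C3D1. Patients stay up to about 2 h longer at those two visits, and the trough tracings there are lost. The comparison with a pre-dose baseline also reflects time of day and possibly food. It is descriptive and would not reliably separate the doses with 20 patients per arm. Change 2 needs only data already collected.

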6.6 Tumour Biopsy

When patient presents with a biopsiable tumour/nodes/metastatic lesion, an on-study tumour biopsy will be performed (only in patients who agree to provide consent for the biopsy). The biopsy will be done after eligibility confirmation and prior to first dose on C1D1. A second biopsy sample will be taken at C3D1.

Tumour tissue collected during the study will be fixed and processed to a FFPE block. Details on shipping the FFPE block to the central genomics lab will be detailed in the laboratory manual

6.7 Serum Cytokines/Chemokines

Correlative serum for cytokines/chemokines (refer Appendix C) will be collected at screening and at the C3D1. Blood samples will be obtained in all patients at baseline and at C3D1. Processed serum samples will be stored at the specified temperature until analysis. The analyses of correlative markers are exploratory evaluation and will not be used to guide treatment decisions in the dose escalation and expanded cohort of the study. See laboratory manual for blood/serum processing instructions.

6.8 End of Trial Treatment (EOT) Visit

All discontinued patients will undergo the end-of-treatment (EOT) assessments within 7 days after the last dose of study drug or discontinuation from the study. Radiological assessment will not be performed if done earlier within 28 days.

CONFIDENTIAL Page 36 of 66

Protocol No. RP6530-2101 Version 1.0, Dated June 29, 2021

6.9 End of Study (EOS) Visit

All patients must be followed up telephonically for adverse events for 30 calendar days after the last dose of study drug. In case of drug related SAE/AE or treatment discontinuation due to adverse event, the patients will be followed till the resolution/stabilization of the AE or 30 days after the last study dose whichever is the earlier.

CONFIDENTIAL Page 37 of 66

| Table 5 : Schedule of Events | | | | | | | | | | |
|---|-----------|----|-----|----|-----|----|---|---|-------------------|-------------------|
| Cycle | Screening | (| C1 | Ó | 22 | С3 | Monthly visits (C4 onward up to 2 year) ¹⁹ | Efficacy Visits (C5, C7, C9 up to 2 year) ²⁰ | EOT ²¹ | EOS ²² |
| Day | D-28 to 0 | D1 | D15 | D1 | D15 | D1 | D1 | D1 | - | - |
| Window period | - | | ±1 | ±1 | ±3 | ±3 | ±3 | ±7 | +7 | +30 |
| Study Days | D-28 to 0 | 1 | 15 | 29 | 43 | 57 | - | - | - | - |
| Informed Consent ¹ | X | - | - | - | - | - | - | - | - | - |
| Demographics ² | X | - | - | - | - | - | - | - | - | - |
| Medical history ³ | X | X | - | - | - | - | - | - | - | - |
| Vitals ⁴ | X | X | X | X | X | X | X | - | X | - |
| Height and weight ⁵ | X | X | X | X | X | X | X | - | X | - |
| Physical examination ⁶ | X | X | X | X | X | X | X | - | X | - |
| ECOG Performance Status | X | X | - | X | - | - | X | - | X | - |
| Complete blood count ⁷ | X | X | X | X | X | X | X | - | X | - |
| Chemistry panel I ⁸ | X | X | X | X | X | X | X | - | X | - |
| Chemistry panel II ⁹ | X | X | - | X | - | X | X | - | X | - |
| HIV, HBV, HCV status | X | - | - | - | - | - | - | - | - | - |
| PT and INR ¹⁰ | X | X | = | X | - | X | - | - | X | = |
| Cytokines/chemokines analysis ¹¹ | X | - | - | - | - | X | - | - | - | - |
| Urinalysis (routine) | X | X | X | X | X | X | X | - | X | - |
| Pregnancy test ¹² | X | X | - | - | - | - | - | - | - | - |
| 12-lead ECGs ¹³ | X | X | - | X | - | X | - | - | X | - |
| Tumour biopsy 14 | X | - | - | - | - | X | - | - | - | - |
| Radiological assessment (CT and/or MRI) 15 | X | - | - | - | - | X | - | X | X | - |
| Bone scan ¹⁶ | X | - | - | - | - | - | - | - | - | - |
| Drug Dispensing ¹⁷ | - | X | - | X | - | X | X | - | - | - |

CONFIDENTIAL Page 38 of 66

Version 1.0, Dated June 29, 2021

| Tenalisib administration ¹⁸ | - | X | X | X | X | X | X | - | - | - |
|--|---|---|---|---|---|---|---|---|---|---|
| Drug compliance | - | X | X | X | X | X | X | - | X | - |
| AE evaluation | X | X | X | X | X | X | X | - | X | X |
| SAE evaluation | X | X | X | X | X | X | X | - | X | X |
| Concomitant medication | X | X | X | X | X | X | X | - | X | X |

Foot notes:

- 1. Patient should be re-consented, if informed consent is obtained > 30 days prior to the initiation of trial treatment. The first day of tenalisib administration will be considered as C1D1.
- 2. Demographic profile will include age, sex and race.
- 3. Detailed history will be taken at screening that includes history of cancer, past history, no of prior therapies and prior medication (in last 4weeks); and other medical history. Patient's medical record must include prior treatments received, dates of administration, response to prior therapies and date of progression.
- 4. Vitals will include pulse (sitting/supine); blood pressure (sitting/supine); respiratory rate and oral temperature. Vitals will be done at pre-dose at all visits.
- 5. Weight will be measured at all visits. Height to be measured at screening only.
- 6. Physical examination will include systemic examination (General Appearance, HEENT, neck, cardiovascular, lungs, abdomen, extremities, neurological, skin, and musculoskeletal). Complete physical examination will be done at screening visit. At subsequent visits, abbreviated examination will be done depending on the assessment of tumour.
- 7. This will include Hb, complete blood count, total leucocyte and differential count and platelet count. Additional investigations will be performed if clinically indicated. Hematology must be done ≤ 7 days prior to initiation of treatment. However, if these initial examinations are obtained within 72 hours of C1D1; they do not have to be repeated.
- 8. Chemistry Panel I include blood glucose, albumin, total protein, total bilirubin, ALP, AST, ALT, GGT, LDH, urea or blood urea nitrogen, creatinine, sodium, potassium, chloride, calcium, phosphorus. These tests must be done ≤ 7 days prior to initiation of treatment. However, if these initial examinations are obtained within 72 hours of C1D1; they do not have to be repeated. These tests will be performed at supplementary visits if clinically indicated.
- 9. Chemistry Panel II includes total cholesterol, TG, LDL, HDL, T3, T4 and TSH. These tests must be done ≤ 7 days prior to initiation of treatment. However, if these initial examinations are obtained within 72 hours of C1D1; they do not have to be repeated. These tests will be performed at supplementary visits if clinically indicated.
- 10. The tests must be done ≤ 7 days prior to initiation of treatment. However, if initial examination is obtained within 72 hours of C1D1; this does not have to be repeated. This test will be performed at supplementary visits if clinically indicated.
- 11. Blood will be collected in all patients for serum cytokine/chemokine estimation at screening (baseline) and at C3D1.
- 12. This is required for women of child-bearing potential. A serum pregnancy test will be performed at screening and 72 hours prior to dosing. Urine pregnancy test will be performed at other visits as indicated.
- 13. ECGs will be performed at screening and C1D1 pre-dose to establish baseline cardiac activity. Additional ECGs will be obtained if clinically indicated. All ECGs will be performed on local equipment.
- 14. A tumour biopsy will be performed in 10-12 patients who have consented for the biopsy. The biopsy will be done after eligibility confirmation prior to the first dose on C1D1. A second tumour biopsy sample will be taken at C3D1.
- 15. CT and/ or MRI will be performed at the time of screening within 28 days of screening. Disease will be re-assessed at C3D1 (± 7 days) and approximately 8 weeks thereafter (± 7 days), and/or at the EOT (not required if done within last 28 days) and/or as clinically indicated (if clinical progression is

CONFIDENTIAL Page 39 of 66

- suspected). If a CR or PR is noted, confirmatory scans should be performed at least 4 weeks after the initial response was first documented. Tumour imaging should remain consistent throughout the study and should include those thought by investigator to best capture status of disease. (Baseline scan, if already available as SOC within 28-days of screening is accepted as part of study protocol). Any other sites at which new disease is suspected should also be appropriately imaged.
- 16. Bone scan will be done at the baseline when progression in bone is suspected. Bone scans need to be repeated only when complete response is reported in target disease or when progression in bone is suspected.
- 17. Tenalisib will be dispensed in a HDPE container having 30 tablets of tenalisib.
- 18. Tenalisib will be administered orally twice a day in 28-days of cycle. Tenalisib will be continued in patients experiencing clinical benefit for 24 months unless progression of disease or toxicity is observed warranting discontinuation of therapy.
- 19. All visits will be done monthly from Cycle 3 onwards for 24 months (e.g. C4, C5, C6.... C26).
- 20. All visits for efficacy assessments will be done at 8-weekly intervals (± 7 days) for 24 months (e.g.C5, C7.... C26).
- 21. All patients will undergo the end-of-treatment (EOT) assessments within 7 days after last dose of study drug or discontinuation.
- 22. Patients must be followed telephonically for adverse events for 30 calendar days after the last dose of study drug.

CONFIDENTIAL Page 40 of 66

